## 4.9 SAFETY ANALYSES

Safety will be assessed through descriptive summaries of adverse events, antibodies to emicizumab, laboratory test results (serum chemistry and hematology, including complete blood count with differential) and vital signs.

For all safety analyses, the summary tables will include data up to the up-titration (if any) only, except if specified otherwise.

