#### **4.5 PREVIOUS AND CONCOMITANT MEDICATIONS**

Use of prior and concomitant medication will be presented by medication class and standardized medication name. Number and percentage of patients and number of medications will be presented. Summary tables on concomitant medications will include all dates (before and after up-titration).

A medication is considered concomitant if the start date/time is on or after the date/time of Original Study Day 1. Otherwise, a medication is considered prior if the end date/time is not missing and is before the date/time of Original Study Day 1. Otherwise a medication is considered prior-concomitant.

All hemophilia medication (collected on the electronic handheld device or the site data entry system) will be reported separately. The number of doses and the cumulative doses will be summarized by category of hemophilia medication. Summary tables for hemophilia medications will include data up to the up-titration (if any) only. If at least 10 patients are up-titrated then the frequency table will also be produced on the period after up-titration.

Also all prior episodic and prophylactic hemophilia medication collected on the hemophilia history page will be summarized separately.

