Only treatment emergent adverse events (starting on or after exposure to study treatment) starting on or before the end of the reporting period will be included in summaries. To define if an AE is treatment-emergent, only the date of the AE will be used (not the time). The end of the reporting period is defined as the end of the 2-year treatment period, for patients who completed the treatment, and as 24 weeks after the last dose of study treatment or 2 years after the first dose of study treatment, whichever occurs first, for patients who early discontinued from treatment. Non-treatment emergent events and AEs starting after the reporting period will be included in the patient listings and flagged but not included in the above summaries. Where an AE start date is partially or fully missing, and it is unclear as to whether the AE is treatment emergent, it will be assumed that it is.

In addition, AEs which start during follow up will be summarized in a separate single table.

Confirmed and suspected COVID-19 AEs will be listed, as well as AEs associated with COVID-19 (i.e. confirmed/suspected COVID-19 AEs and AEs with onset from -7 days to +30 days from the start of a confirmed COVID-19 AE).

Notes:

Tables presented will contain both counts of patients and events (at SOC level only). Patients who have multiple events in the same system organ class and preferred term will be counted only once in the patient counts.

AEs will be coded using MedDRA. The version of the dictionary used will be updated throughout the study.

In addition, a summary of non-serious AEs occurring in 5% or more of patients will be provided (for Disclosure purposes).

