### Adverse event rate per 100 patient-years

Adverse events per patient years will be calculated for all grade AEs, SAEs, grade  $\geq 3$  AEs, TMA, thromboembolic events (TE) and TMA+TE combined. For each category of events, multiple occurrences of the same event (Preferred term) in the same patient will be counted multiple times.

The adverse event rate per 100 patient-years is computed as follows:

$$\text{AE Rate} = (\text{Number of AEs observed} / \text{Total patient-years at risk}) * 100$$

Total patient years is computed as follows:

Total patient-years at risk is the sum over patients of the time intervals (in years) between start of study therapy (study day 1) and the end of follow up or up to the cutoff whichever is earlier. This approach assumes that during an adverse event, patients remain at risk for additional events.

The 95% confidence interval for the event rate is calculated using the following method. Assume that we observe Y events over a total of T person-years at risk.

Exact confidence interval:

If  $\text{chisq}(p, df)$  is the quantile of the upper tail probability of the  $\chi^2$  distribution on df degrees of freedom, then the lower and upper bounds (LB, UB) of the exact  $(1 - \alpha/2)$  level interval are given by:

$$\text{LB} = \text{chisq}(p = \alpha/2, df = 2Y) / (2T)$$

$$\text{UB} = \text{chisq}[p = 1 - \alpha/2, df = 2(Y + 1)] / (2T)$$

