### Details on AE reporting

A flag will indicate to which study phase an AE belongs to: before therapy, treatment period (initial treatment 3 mg/kg/week SC for 4 weeks, followed by 1.5 mg/kg/week SC) up-titration period, or follow up (general section 4.1).

All treated patients will be analyzed by descriptive summaries of the AEs by SOC mapped term (by descending frequency) and by Preferred Term (PT) (by descending frequency).

Multiple occurrences of the same AE (by PT) per subject are counted only once unless defined otherwise, this also applies for Bleeds which are reported as SAE. For Total number of Events multiple occurrences of the same AE on an individual are counted separately. Symptoms of Injection Site Reactions are summarized separately. For some specific adverse event types, an additional table will display instances where multiple occurrences of the same AE in the same patient are all counted (for Disclosure purposes).

A listing of AEs will be generated for patients with at least one up-titration. If at least 10 patients are up-titrated then a summary table will be produced on the period after up-titration.

A standard summary table is produced for AEs falling into SMQ-hemorrhage (wide).

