##### Notes:

The AESI categories and preferred terms to be summarised will be identified from the project level list which covers the categories defined for this study, if applicable; or based on the investigator's judgement as collected in the eCRF otherwise.

In addition, potential drug-induced liver injuries will have to meet the Hy's Law criteria, based on laboratory results:

- ALT or AST > 3 × baseline
- and
- Total bilirubin > 2 × ULN (of which ≥35% is direct bilirubin)

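### SAP 4.9 stops safety summary tables at up-titration by default and does not clearly exempt the main adverse event tables, although the primary endpoint is all adverse events

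*SAP*

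**What the plan says.** The general rule in SAP 4.9 is: "For all safety analyses, the summary tables will include data up to the up-titration (if any) only, except if specified otherwise".

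SAP 4.9.2 then names the incidence tables (all AEs, serious AEs, grade 3 and above, AEs of special interest, fatal AEs and others) and does not say which dose periods they cover. Its inclusion rule is that only treatment-emergent AEs "starting on or before the end of the reporting period will be included in summaries". That period ends at the end of the 2-year treatment period for completers. For early discontinuers it ends 24 weeks after the last dose or 2 years after the first, whichever is earlier. Up-titration is not mentioned.

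Under the details on AE reporting, the SAP adds two displays for up-titrated patients. One is an AE listing, produced whatever their number. The other is a table that depends on that number: "If at least 10 patients are up-titrated then a summary table will be produced on the period after up-titration".

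For AEs of special interest, SAP 4.9.2.1 says only where the terms come from: "The AESI categories and preferred terms to be summarised will be identified from the project level list". For the AE rate per 100 patient-years, person-time runs between "start of study therapy (study day 1) and the end of follow up or up to the cutoff whichever is earlier", so it does not stop at up-titration.

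The primary endpoint in SAP 2.2 and protocol 6.4 is the incidence and severity of all AEs. Protocol 6.4 analyses all safety variables in the safety population and sets no limit by dose period.

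**The concern.** Up-titration is part of the regimen that the protocol allows, so AEs on the higher maintenance dose belong to the primary endpoint. A default that removes them from the main tables conflicts with that endpoint unless it is lifted, and the text does not clearly lift it.

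Two programmers could therefore build the primary tables differently. A reader of the report could not tell whether a thrombotic microangiopathy (TMA) or thromboembolic event after up-titration is in the incidence table. That table could also cover a different period from the rate per 100 patient-years for the same event type.

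**Working it through.** **Which reading does the text support?**

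1. SAP 4.9 is an explicit rule about dose period.
2. The inclusion rule in 4.9.2 fixes treatment emergence and the end of the AE window. It is worded as a restriction and is silent on dose period. It can be read as the exception that 4.9 allows for, but it does not say so.
3. A listing for up-titrated patients, plus a later-period table only from 10 patients upward, is what one would plan if the main tables stopped at up-titration.
4. SAP 4.5 states that the concomitant medication tables cover both periods. The AE tables carry no such statement.
5. The rate is introduced with "Assume that we observe Y events over a total of T person-years at risk". T runs past up-titration, so Y most naturally does too. Truncated incidence tables would then differ in period from the rates.

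**The plan's own figures.** Exact Clopper-Pearson limits for 5, 10, 20 and 30 of 200 come to 0.82–5.74%, 2.42–9.00%, 6.22–15.02% and 10.35–20.72%. They match protocol Table 14 and SAP Table 1.

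**How many patients might be up-titrated?** The documents give no figure for this trial. As an assumption, take the 2 of 109 reported for study BH29884 in protocol 1.2.2.3. It is a weak proxy: that study allowed up-titration only after 24 weeks, and 18 of the 109 started without prophylaxis.

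- Expected number: 200 × 2/109 = 3.7.
- Clopper-Pearson for 2/109: 0.22% to 6.47%, which is 0.4 to 12.9 per 200.
- Chance of reaching the 10-patient trigger, P(X ≥ 10) with X ~ Binomial(200, p):

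| p | P(X ≥ 10) |
|---|---|
| 2/109 | 0.4% |
| 3% | 8% |
| 4% | 28% |
| 6.47% | 84% |

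**How much would truncated tables miss?** Assume n patients are up-titrated at month 6 of 24, with constant hazard and the same risk as other patients. Patients whose first event falls after up-titration number on average n × [(1 − p)^0.25 − (1 − p)], where p is the 24-month incidence.

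| True incidence | Omitted, n = 4 | Omitted, n = 9 |
|---|---|---|
| 2.5% | 0.07 | 0.17 |
| 5% | 0.15 | 0.33 |
| 10% | 0.30 | 0.67 |
| 15% | 0.44 | 0.99 |
| 5/189 (TMA or thromboembolic, pooled earlier trials) | 0.08 | 0.18 |

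- True 15%: (30 − 0.44)/200 = 14.8% and (30 − 0.99)/200 = 14.5%.
- True 2.5%: about 2.5% and 2.4%.
- Varying the timing at 15%: 0.14 omitted (n = 4, month 18) to 1.17 omitted (n = 9, month 3).
- At 5/189, the chance that at least one such patient is omitted is 8% (n = 4) to 16% (n = 9). This may be too high, because those events followed aPCC amounts that this protocol says to avoid.

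**One-event scenario (not an estimate).** If the only TMA or thromboembolic event came after up-titration, the incidence table would show 0/200 (95% CI 0 to 1.8%) instead of 1/200 (0.01% to 2.8%).

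**If the default also cut the rate numerator** (the less likely reading): with 400 patient-years in total, time after up-titration is 4 × 1.5 = 6.0 or 9 × 1.5 = 13.5 patient-years. Rates would be 6.0/400 = 1.5% to 13.5/400 = 3.4% too low.

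**The case against.** The best counter-argument is that a specific rule overrides a general one. SAP 4.9.2 says which AEs enter the summaries and names what stays out: AEs that are not treatment-emergent and AEs after the reporting period. Events after up-titration are not on that list, so the main tables may already be meant to run in full. This reading is possible, and if it is the intended one the fix only writes it down. It is still not clear text: the clause never mentions up-titration, whereas 4.9 does.

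Other points carry some weight:

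- The listing and the conditional later-period table could also supplement full-period tables. The 4.5 wording lies outside the 4.9 default. Both are supporting evidence for truncation, not proof.
- Separating dose periods is a deliberate choice, applied by default to efficacy (SAP 4.6) and immunogenicity (SAP 4.8) as well. That is reasonable there, but here the primary endpoint is all AEs.
- Coverage elsewhere is good. On its natural reading the rate table counts TMA and thromboembolic events after up-titration, AEs that start in follow-up have their own table, AEs of up-titrated patients are listed, and deaths are listed with cause. Events in the first 4 weeks at 3 mg/kg/week are in the main tables in any case.
- Incidence and rate differ by design, since one counts patients and the other counts events. A difference in period would come on top of that and would be unexplained.

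These points limit the severity. They do not remove the conflict between the stated default and the endpoint.

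**Conclusion.** The point holds, as a minor one. The default in SAP 4.9 removes events after up-titration from the safety summary tables, and the main AE, serious AE, fatal AE and special-interest tables are not clearly exempted. Taken literally, the primary incidence tables would not show all AEs in the safety population.

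The expected effect is below one patient per AE type in the base scenarios. It is small for common AEs and could decide between zero and one for a rare event of special interest. These sizes rest on an assumed 4 to 9 up-titrations at month 6, constant hazard and equal risk, none of which the documents give. The wording problem does not depend on them. Nothing is lost from the listings.

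**What to change.** - In SAP 4.9 and 4.9.2, state that the main AE, serious AE, fatal AE and special-interest tables run from first dose to the end of the reporting period defined in 4.9.2, regardless of up-titration.
- In the section on rates per 100 patient-years, add one sentence that events and patient-years come from the same window.
- Present results before and after up-titration as a supplementary display, using the study-phase flag already planned. This keeps the separation by dose period.
- For laboratory shift tables, confirm that the during-treatment interval in 4.9.5, with the treatment period in 4.1, overrides the 4.9 default.
- Optionally, produce a table of serious AEs and AEs of special interest after up-titration whatever the number of patients.

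The cost is two or three sentences and possibly a few extra tables from data already collected and flagged. Incidence figures may become slightly less favourable.

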#### **4.9.1 Exposure of Study Medication**

In addition, as part of the safety evaluation, additional assessments will be summarized descriptively as follows:

- Cumulative study medication doses, dose modifications (delays and interruptions), and duration of exposure (continuous and categorized)
- Administration injection site (listed only)
- Patients with up-titrated dose.
- Dose intensity (compliance with respect to emicizumab intake: planned vs. received), for initial and maintenance phases separately

A dose is considered to be missed if there is an interval of >10 days between two doses. A patient who received < 90% or >110% of the planned dose is considered to have received a lower or higher dose than the planned dose, respectively. The planned dose is calculated using the last patient's weight before or at the day of the emicizumab injection and the dose per kilogram according to protocol.

The emicizumab dose is reported by the patient in ml. In order to convert the ml entered by the patient to mg, the following formula should be applied:

$$x \text{ ml} \times 150 \frac{\text{mg}}{\text{ml}} = y \text{ mg of emicizumab}$$

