If the patient forgets or cannot administer *emicizumab* ~~the study medication~~ on the scheduled dosing day, *emicizumab* ~~the study medication~~ should be administered *as soon as possible before the day of the next scheduled dose, and then the patient should resume the usual weekly dosing schedule. Do not double doses to make up for a missed dose. All four loading doses of 3 mg/kg should be taken, even if this is done over a period or more than four weeks. as soon as possible within a window of 3 days from the scheduled dosing date. If more than 3 days has passed, the missed dose should be skipped, and the patient should take their next dose at the next scheduled time. If this scenario occurs, study medication dosing should be resumed in accordance with the original dosing schedule.*

Any overdose or incorrect administration of *emicizumab* ~~the study drug~~ should be noted on the Study Drug Administration eCRF. Adverse events associated with an overdose or incorrect administration of *emicizumab* ~~the study drug~~ should be recorded on the Adverse Event eCRF. [Section 5.3.5.12](#) summarizes available safety data related to overdosing of emicizumab.

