Medication administration errors during training will be documented in the electronic Case Report Form (eCRF). If necessary, patients or their HCP may choose to continue administration of *emicizumab* within the clinic. Compliance in the home setting is to be monitored at each site by reviewing reported hemophilia medication use and recording collected used and unused vials.

If the patient forgets or cannot administer *emicizumab* on the scheduled dosing day, *emicizumab* should be administered *as soon as possible before the day of the next scheduled dose, and then the patient should resume the usual weekly dosing schedule. Do not double doses to make up for a missed dose. All four loading doses of 3 mg/kg should be taken, even if this is done over a period or more than four weeks.*

Any overdose or incorrect administration of *emicizumab* should be noted on the Study Drug Administration eCRF. Adverse events associated with an overdose or incorrect administration of *emicizumab* should be recorded on the Adverse Event eCRF. [Section 0](#) summarizes available safety data related to overdosing of *emicizumab*.

Patients and/or caregivers will be provided with alert cards, which they will be requested to carry at all times. These will include guidance on recognizing the signs/symptoms of thromboembolic events or allergic/anaphylactic/anaphylactoid reactions and how to obtain emergency care. In addition, alert cards are designed to notify non-study HCPs that *emicizumab* will interfere with certain coagulation laboratory tests (see the Investigator's Brochure for more information) and that the investigator should be contacted for assistance in interpreting the test results.

Guidelines for dosage modification and treatment interruption or discontinuation are provided in [Section 5.1.1](#).

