## Appendix 1 Schedule of Activities (cont.)

Visits	Screening	Treatment											Early Termination / Study Completion	Safety Follow-up Visit [a]	
	Wk -4 to Wk 0	Wk 1	Wk 2	Wk 3	Wk 5	3 m	6 m	9 m	12 m	15 m [b]	18 m	21 m [b]	Unscheduled visit	2 years	
Time Window, days			± 2	± 2	± 2	± 7	± 7	± 7	± 14	± 14	± 30	± 30		± 30	
Bone and joint biomarker assessment (fasting) [s,x]		x					x				x			x	
Additional laboratory assessments [y]		For breakthrough bleeds treated with bypassing agents													
Emicizumab administration		Weekly subcutaneous injection													

d=day; eCRF=electronic Case Report Form; EQ-5D-5L=EuroQoL Five-Dimension-Five Levels Questionnaire; FVIII=Factor VIII; Haem-A-QoL=Hemophilia Adult Quality of Life Questionnaire; Haemo-QoL-SF=Hemophilia Quality of Life Short Form; HIV=human immunodeficiency virus; HRQoL=Health-Related Quality of Life; m=months (based on calendar months); PD=pharmacodynamic; PK=pharmacokinetic; Wk=week

Notes: the maximum allowable time between Screening and enrollment is 4 weeks; if the elapsed time between Screening and enrollment is more than 4 weeks, Screening must be repeated.

Except for the bleed/medication records, all other patient data will be collected during clinic visits.

- b. Patients who discontinue emicizumab prior to the completion of the 2-year treatment period will undergo a Safety Follow-up Visit 24 weeks after the patient's last emicizumab dose or at 2 years after emicizumab treatment start, whichever occurs first.
- c. Optional visits, as per the investigator's discretion.
- d. **Written informed consent** must be obtained before any study-specific screening tests or evaluations are performed. For adolescents (i.e., patients who are 12–17 years of age), an Informed Assent Form will be completed instead. Parents or caregivers of adolescents will also complete an Informed Consent Form. The enrollment form will be completed after informed consent and/or assent is obtained. All screening evaluations must be completed and reviewed to confirm that patients meet all eligibility criteria before enrollment.

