## STATISTICAL ANALYSIS PLAN HISTORY

SAP Version / Date	Description
Version 1.0 / 11 June 2018	Initial version.
Version 2.0 / 6 December 2018	
 
• Revision based on protocol amendment v3.0 dated 09MAR2018: population for patients with surgery on-study added (Section 4.2.5) and analyses on patients with surgeries on-study added (Sections 4.4 and 4.9.4).
 
• Population for efficacy analyses updated to ITT instead of Safety (Section 4.6), for consistency with protocol.
 
• Clarifications added on the study periods (before up-titration, after up-titration, both) to be included in the analyses.
 
• Updates done for consistency with Haven-1 and Haven-4 studies: Definition of efficacy period (Section 4.1); Definition of prior / concomitant medications (Section 4.5).
 
• Addition of analyses done for Haven-1 and Haven-4 studies: Compliance analyses for questionnaires (Section 4.6.1.7); Analysis of the number of days hospitalized (Section 4.6.8).
 
• Updates to the analysis of adverse events (Section 4.9.2): clarification of the reporting period, list of AESIs revised as per protocol.
 
• Details on the PK analysis removed as it will be described in a separate SAP.
 

Version 3.0 / 5 November 2020	
 
• Definition of treated joint bleeds revised for consistency with Haven-1 and Haven-4 studies: aura criterion removed (Section 2.2.2.7)
 
• Definition of positive ATA patients updated for consistency with Haven-1 and Haven-4 studies (Section 4.8)
 
• Definition of TEAEs clarified (Section 4.9.2)
 
• Section on analysis of surgeries revised (Section 4.9.4)
 
• Section on analysis of biomarkers revised (Section 4.10)
 
• Analyses on impact of COVID-19 added (Section 4.3 and 4.9.2)
 
• Details on the PK analysis added (Section 4.7)
 

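### The SAP's missed-dose flag (more than 10 days between doses) does not match the current late-dose rule, so doses given 4–6 days late as allowed can be counted as missed

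*SAP*

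**What the plan says.** SAP section 4.9.1 (Exposure of Study Medication) states: "A dose is considered to be missed if there is an interval of >10 days between two doses". It gives no derivation of the 10 days. The same section separately lists a summary of dose modifications, covering delays and interruptions, and a compliance measure: "Dose intensity (compliance with respect to emicizumab intake: planned vs. received), for initial and maintenance phases separately". It also classes patients as having received a lower or higher dose than planned at <90% and >110%.

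The protocol's Schedule of Activities (Appendix 1) gives the regimen as "Weekly subcutaneous injection". Under current protocol section 4.3.2.1, a dose not taken on its scheduled day is to be given "as soon as possible before the day of the next scheduled dose, and then the patient should resume the usual weekly dosing schedule". The same paragraph adds "Do not double doses to make up for a missed dose" and "All four loading doses of 3 mg/kg should be taken, even if this is done over a period or more than four weeks".

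The protocol's summary of changes for version 3 shows, as deleted text, that a late dose formerly had to be given "within a window of 3 days from the scheduled dosing date". The SAP history describes SAP version 2.0 as "Revision based on protocol amendment v3.0 dated 09MAR2018". The current SAP is version 3.0 and carries the 10-day rule.

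**The concern.** The SAP rule infers omission from the gap between two recorded injections. That works only if the longest gap the protocol allows without an omission is shorter than the shortest gap with one. The protocol now tolerates lateness of up to 6 days in a 7-day cycle, and the two kinds of gap overlap.

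A missed-dose count would then include injections that were given within the protocol's own rule. In the same section a 4–6-day delay would be both a delay and a missed dose. Exposure and compliance are part of the safety evaluation in a trial whose primary objective is safety, so a reader of the study report could take the count as evidence of worse adherence than occurred. Loading doses are affected in the same way, because the protocol expects all four to be taken even if that takes longer than four weeks.

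**Working it through.** **Inputs.** Planned interval 7 days (protocol Appendix 1). Allowed lateness L = 0 to 6 days, then back to the usual weekly day (current protocol section 4.3.2.1). Flag if the interval exceeds 10 days (SAP section 4.9.1). The deleted 3-day window is used only to trace where 10 may come from.

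**Formula.** For two injections L1 and L2 days late with m scheduled doses omitted between them:

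interval = 7(m + 1) + (L2 − L1).

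**1. Reproducing the 10 days.** With the deleted window (L = 0–3), the interval without an omission is 7 ± 3, that is 4–10 days; with one omission it is 14 ± 3, that is 11–17. These do not overlap, and >10 separates them exactly.

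**2. Current rule.** With L = 0–6, the interval without an omission is 7 ± 6 = 1–13 days; with one omission it is 14 ± 6 = 8–20. They overlap at 8–13 days.

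**3. One late dose after an on-time dose.** Column 2 is the interval up to the late dose, 7 + L. Column 4 is the interval if the next dose is then omitted and the following one is on time, 14 − L.

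| L | 7 + L | Flagged? | 14 − L | Flagged? |
|---|---|---|---|---|
| 1 | 8 | no | 13 | yes |
| 2 | 9 | no | 12 | yes |
| 3 | 10 | no | 11 | yes |
| 4 | 11 | yes | 10 | no |
| 5 | 12 | yes | 9 | no |
| 6 | 13 | yes | 8 | no |

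If nothing is omitted, L = 4–6 gives one false flag. If the next dose is omitted, every row gives one flag for one omission. For L = 4–6 the flag falls on the wrong dose, but the total is right.

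**4. When a single omission escapes altogether.** The interval spanning it must be at most 10, so the dose before it must be at least 4 days late; and that lateness must have been reached in steps of at most 3 days, or an earlier interval is flagged. Example: 2 then 4 days late, then an omission, then on time gives 7 + 2 = 9, 7 + 2 = 9 and 14 − 4 = 10, with no flag. Of the 7 × 7 = 49 patterns of two doses each 0–6 days late, followed by one omission and an on-time dose, 6 give no flag, 31 give one and 12 give two.

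**5. Moving the cut-off.** A cut at >13 days removes the false flags, but then an omission after a dose only 1 day late (14 − 1 = 13) is not detected.

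**6. Size.** Two years of weekly dosing is about 2 × 52 = 104 doses. If 1–5% are 4–6 days late (assumed), that is 1.04–5.2 doses per patient. This is an upper bound on false flags from such doses, because the preceding dose matters too: 4 days late after 1 day late gives 7 + 3 = 10, not flagged. A simulation of 4,000 patients on assumed rates, with lateness uniform on 1–6 days, gives per patient:

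| Late | Missed | True missed | Flags | False flags | Undetected missed intervals |
|---|---|---|---|---|---|
| 5% | 2% | 2.05 | 4.3 | 2.4 | 0.04 |
| 20% | 5% | 5.1 | 12.3 | 7.8 | 0.40 |

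None of these rates is in the documents. The direction does not depend on them closely: over-counting dominates in both rows.

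**The case against.** The strongest case against is that little hangs on the flag, and this largely stands. All analyses are descriptive. A dose given late is still a received dose, so dose intensity and the <90%/>110% classes, which compare received with planned amounts, are untouched. A reader might infer that the compliance table as a whole is wrong; the SAP does not support that, because neither measure is defined by the interval.

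A reader might also infer that the count is equally wrong in both directions. It is not. An omission after a dose 1–3 days late is still flagged, and after an isolated dose 4–6 days late the total is still one flag for one omission. A net under-count of a single omission needs lateness that builds up.

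A third tempting reading is that the flag underlies the interpretation of bleeds and trough concentrations. No section says so: the bleed model uses the efficacy period as offset (SAP section 4.6.1.1) and troughs are summarised by timepoint (SAP section 4.7).

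Finally, the protocol itself uses the term missed dose loosely, for any dose not taken on its day, so the SAP rule could be read as a label for long gaps. That is a fair point about wording. It does not rescue a rule that, as written, counts an injection that was given as one that was not.

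**Conclusion.** The mismatch is real and limited. The SAP's missed-dose flag conflicts with the current protocol: a dose given 4–6 days late after an on-time dose is allowed, yet counted as missed. The missed-dose count is mainly too high, by at most about 1–5 per patient over two years if 1–5% of doses are that late. This rests on that assumed rate and on no injections being given early. A net under-count of a single omission is possible only after successive late doses.

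That the 10 days is a leftover from the deleted 3-day window is an inference: the arithmetic fits exactly, but no document says so. The conflict between the two current texts does not depend on it. The error is confined to the missed-dose flag and count, and no primary endpoint is affected. It is a minor correction, worth making because it is cheap.

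**What to change.** Reconcile SAP section 4.9.1 with protocol section 4.3.2.1 by replacing the interval rule with a schedule-based one:

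- Allocate each recorded injection to one scheduled weekly dose, allowing for doses given early and for a loading phase longer than four weeks.
- Count a scheduled dose as missed only if no injection is allocated to it before the day of the next scheduled dose.
- Report doses given late within that window under the delays summary already planned.

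The allowance for early doses is needed. A plain rule that looks for an injection from the scheduled day to the day before the next one would call the day-7 dose missed when injections fall on days 0, 6 and 14, although it was given one day early. Early injections are foreseeable, since the Week 2, 3 and 5 visits have windows of ±2 days.

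This changes only an analysis label and takes no position on the dosing rule. Patients already record emicizumab use at least weekly, so no new data are needed. The cost is a short SAP revision and somewhat more programming to anchor each patient's schedule.
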